8.8 Loss to Follow-up

Trial follow-up will be in part via routinely collected data downloaded in a bespoke trial download by each recruiting site; in part via paper CRFs completed by the trial RNs and RPTs; and in part via LRSQs collecting Parent Reported Outcome Measures (PROMs) at 6 and 12 months post randomisation. Where a patient is lost to follow-up before the relevant time point (e.g. lost due to transfer to another hospital), contact will initially be attempted by the trial RNs and the PI at each site. Wherever possible, information on the reason for loss to follow-up will be recorded.

8.9 Trial Closure

The end of the trial is defined to be the date on which data for all participants are locked and data entry privileges are withdrawn from the trial database. However, the trial may be closed prematurely by the Trial Steering Committee (TSC), on the recommendation of the Independent Data and Safety Monitoring Committee (IDSMC).

Individual sites may be closed to recruitment prior to their intended recruitment end date if the Trial Management Group (TMG) have concerns about their capacity or capability to deliver the trial, or for operational reasons whereby resources are better used at sites with better capacity to recruit. At the point of closure to recruitment all sites will be required to undertake closedown activities which include but are not limited to: a review of their Investigator Site File (ISF), a count of all completed CRFs and completed data queries. Pls will also be required to sign-off the CRF for each participant, any changes to the data, a closedown checklist and their site delegation log.

IRAS 220853 Page **43** of **87**

9 TRIAL TREATMENT/INTERVENTIONS

9.1 Introduction

The intervention being trialled is Endotracheal poractant alfa (Curosurf®, porcine lung phospholipid fraction supplied at 80mg/mL).

Curosurf® is a standard natural surfactant treatment prepared from porcine lungs for intratracheal administration and containing almost exclusively polar lipids, in particular phosphatidylcholine. Endotracheal poractant alfa is licensed for use in the UK for the treatment of Respiratory Distress Syndrome (RDS) or hyaline membrane disease in newborn babies (neonates). It is being used as an investigational medicinal product (IMP) on the BESS trial (UK licence, new indication).

Three small studies of surfactant use in infants with bronchiolitis have raised no safety concerns, however BESS will be the first large, randomised study of any surfactant for the treatment of bronchiolitis of infancy (3). As neonatal RDS is caused by surfactant deficiency, and the viral infections that cause bronchiolitis of infancy also cause surfactant deficiency (which we aim to treat with poractant alfa), we expect that the well tolerated safety profile of use in RDS in neonates will be reflected when using surfactant to treat bronchiolitis in infants.

Participants will be randomised equally to receive either endotracheal poractant alfa or air-placebo in a sham procedure. Participants randomised to receive endotracheal poractant alfa will receive a first dose of 200mg/kg, repeated 12 hourly at 100mg/kg, to a maximum of 3 doses. This is in line with the manufacturer's summary of product characteristics (SPC). Participants randomised to the placebo will receive an identical series of up to three procedures (while intubated) using air as the placebo.

9.2 Arm A – Endotracheal Poractant Alfa at 200mg/kg (first dose), with up to two further doses at 100mg/kg

9.2.1 Formulation, Packaging, Labelling, Storage and Stability

Generic name: Endotracheal poractant alfa

Brand name: Curosurf®

Supply and distribution: Chiesi Farmaceutici S.p.A (Chiesi) will supply Curosurf® via a third-party distributor and will provide appropriate certificates of analytical conformity. Additional shipments during each season will be managed by the distributor contracted by Chiesi, via an automated webbased system.

Packaging: Labelled holder containing one labelled glass vial with a blue topper.

Formulation: Each vial contains 3ml volume of poractant alfa at a concentration of 80mg/ml.

IRAS 220853 Page 44 of 87

Labelling: Vials will be labelled by Chiesi in English and in compliance with the detailed guidance provided in annex 13 of the European Union (EU) Good Manufacturing Practice (GMP) guide. Each vial will be labelled and used for BESS trial use only.

Storage: The PI or delegated research team member will be responsible for the safe storage of all vials assigned to the BESS trial, in a safe place with restricted access (usually a designated drug room on the PICU). Poractant alfa will be stored between 2°C and 8°C, in a separate drug fridge specifically for use in the trial, protected from light in the original packaging.

Stability: Curosurf® has an unopened shelf life of 18 months. Each vial is for single use only.

9.2.2 Preparation, Dosage and Administration of Study Treatment/s

Dosage: An initial dose of 200mg/kg, with two further doses of 100mg/kg at 12hrs and 24hrs if indicated.

200mg/kg is 200milligrams of poractant alfa per kilogram of body weight. 100mg/kg is 100milligrams of poractant alfa per kilogram of body weight. The participant's weight will be detailed on the prescription in kilograms and the prescribing clinician will calculate the appropriate dose and number of vials needed for that participant.

Preparation: Poractant Alfa suspension is refrigerated, so before use each vial must be warmed up slowly to room temperature e.g. keeping it in hands for 5-10 minutes and gently turned upside down, without shaking, avoiding the formation of foam. Artificial warming methods should not be used. The entire contents of the vials of poractant alfa suspension should be slowly withdrawn into a plastic syringe through a large-gauge needle and the excess poractant alfa discarded. A second person must be witness to the drawing up of the poractant alfa to assist and to check that the volume drawn up is the amount prescribed. Once the prescribed volume has been drawn into the syringe, an opaque paper shield should be applied to the syringe in order to maintain blinding of staff and/or parents at the bedside.

At this stage the appropriate equipment should also be prepared for conducting tracheal toilet and BAL.

Tracheal toilet (and, where scheduled, BAL) must be conducted prior to administration of the intervention.

The use of muscle relaxant prior to tracheal toilet, BAL and or administration of the intervention is at clinical discretion.

Administration: Either with the infant connected to the ventilator, or momentarily disconnected with hand-bagging, the syringe filled with Poractant Alfa suspension will be connected to a 5-French catheter end-hole inserted into the endotracheal tube (ETT) for ventilation. Passing the catheter through the suction or side port into the ETT and advancing the catheter aiming to have the tip of the catheter placed just beyond the tip of the ETT. The insertion length should be calculated from the known length of the ETT (typically cut to reduce dead space) plus the distance from the end of the cut edge of the ETT to the suction/side port). The intervention will be given slowly as a single bolus directly into the lower trachea (recommended over 0.5 to 3 minutes). From there it disperses through ventilation cycles into the peripheral lung tissue where the excipient (buffered 0.9% sodium chloride) is absorbed in the alveoli and the surfactant phospholipid is deposited.

The infant should be stabilized before surfactant administration and their head placed in the neutral position (head and body in alignment without inclination).

IRAS 220853 Page **45** of **87**

Before starting the procedure and throughout it, infants must have cardiorespiratory monitoring: oxygen saturation and heart rate continuously through pulse oximetry, blood pressure measurement either continuously in presence of an arterial catheter or intermittently if no arterial line is in place. The first dose at 200 mg/kg will be followed up by two further doses at 100 mg/kg at approximately 12-hour intervals and the exact time and actual volume of each administration will be noted in the medical notes and appropriate section of the CRF.

No suctioning of the airways should be performed for two hours after each surfactant instillation unless the treating physician deems this appropriate, in which case this will be noted in the medical notes and appropriate section of the CRF.

9.2.3 Specific Restrictions

The effect of co-administration of poractant alfa with other agents is not known. Do not administer poractant alfa concomitantly in the same intratracheal bolus with other agents.

9.2.4 Overdose

Overdose may occur if the wrong patient weight has been supplied to the prescribing clinician, an incorrect weight is used in the calculation or the calculation has been done incorrectly. There have been no reports of overdose following the administration of Curosurf® however, in the unlikely event of an accidental overdose that causes clear clinical effects on the infant's respiration, ventilation or oxygenation, as much of the suspension should be aspirated as possible, as per the SPC. Special care must be taken by all site team members to avoid overdosing, noticeably the prescribing clinician and the staff members drawing up the poractant alfa for administration. In the event of identification of an overdose, unblinding should occur and the participant will be closely observed for any adverse events (AE). The site team should notify the CTRC of the event and examine the reasons for the event occurring to ensure that it does not happen again. The CTRC will log any overdosing events as protocol deviations.

9.2.5 Temperature Compliance

Temperature deviations at site will be identified by the regular completion of a trial-specific temperature monitoring log. The PI or delegated member of staff will check the fridge used to store stocks of poractant alfa for use in BESS **daily** and will alert the CTRC if a temperature deviation has occurred. Temperature checks will be recorded on a Temperature Monitoring Log.

Poractant Alfa shipment and storage conditions:

Poractant Alfa (Curosurf®) Suspension 80 mg/ml to 3ml vial	+2°C to +8°C	Up to +25°C for maximum cumulative 96hrs
--	--------------	--

Unopened vials of Curosurf® that have warmed to room temperature can be returned to refrigerated storage **within 24hours** for future use, **if** this is the first time that they have warmed. Vials that have been removed from the fridge and been allowed to warm to room temperature for a second time **must not be used**, but should be retained for accountability checks at the end of each season.

Temperature compliance during shipment will be checked by the local site Pharmacist on receipt of the IMP. The local Pharmacist will review the temperature curves/logs from the calibrated

IRAS 220853 Page **46** of **87**

temperature logger used during IMP shipment and will check for any out of range values. If an out of range temperature is identified, the local Pharmacist will inform the CTRC within 48 hours. It is the responsibility of the CTRC to inform Chiesi, who will then notify the Chiesi R&D Quality Assurance GMP Unit & Project Partners (R&D QA-GMP).

If the out-of-range temperature deviation does not affect the quality and safety of the products, a declaration of usability will be issued and signed by R&D QA-GMP and sent back to the CTRC. CTRC will then authorise the trial site to use the vials in question.

If the products are judged not suitable for use, Chiesi R&D QA-GMP will inform the CTRC to permanently suspend the use of the affected vials. Any vials not used due to temperature deviations will be retained for accountability checks at the end of each season before being sent for destruction.

9.2.6 Accountability Procedures for Trial Treatments

The PI is responsible for the management of poractant alfa to be used for the trial. Trial IMP should be stored in the original packaging to protect from light, in a locked, secure, refrigerated storage facility with access limited to those individuals authorized to dispense or administer the trial IMP. Initial supply of the trial IMP will be to the site Pharmacy. The site Pharmacists are responsible for dispensing stock to a secure drug room on the PICU for more immediate access by the research team. Pharmacists must release the trial IMP to PICU in sequential order by the medication numbers on the labels to ensure the Randomisation System can allocate trial IMP with the shortest shelf life first. No surfactant material supplied for this trial is to be used for any other purpose.

Accountability logs will be maintained by the PI, pharmacist or delegated research team member, which will include a signed account of all the vials of Curosurf® received from the distributor, the vials dispensed to and returned from PICU, with the vials and volume used for each randomised patient.

All completely used vials will be retained at the site until the conclusion of the recruitment season. Each vial is for single use only. Any leftover unused medication is to be retained for drug accountability. Partially used vials present a risk of confusion and sharps injury, so all partially used vials will be disposed of within the PICU as per local Trust standard procedures. Disposal of partially used vials will be logged for accountability checks.

At the conclusion of each recruitment season, the PI, pharmacist or delegated individual shall conduct and document a drug supply (used and unused) inventory. An explanation will be given for any discrepancies.

After the inventory is reconciled at the end of each season and only once the CTRC have given the site authorisation on behalf of the sponsor, remaining unused vials of Curosurf® maybe disposed of directly by the Pharmacy of the involved trial site. Unused vials with an expiry date during or after the next season will be retained. Documentation assuring the unused vials were sent off-site for destruction, as per standard Trust procedures will be provided. This must be signed by two delegated members of staff filed in the Pharmacy site file, with a copy returned to the CTRC for storage in the Trial Master File.

IRAS 220853 Page **47** of **87**

9.2.7 Assessment of Compliance with Study Treatment/s

Each vial of Curosurf® will be designated by code number and the actual volume of instilled test treatment will be noted in the hospital chart and on the CRF of the study.

The completely used vials will be kept in a sealed labelled plastic box/envelope with patient's randomisation number/initials until the end of the season for accountability checks. There will therefore be three "final" accountability checks at each site, one at the end of each recruitment season.

9.3 Arm B - Placebo

Placebo: Air via an identical series of 3 doses in a sham procedure.

Dosage and preparation: Air should be drawn into a syringe at the same volume of 200mg/kg for the first dose and 100mg/kg for the second and third doses (if required), as per the instructions for poractant alfa dose calculations assuming the intervention is provided at 80mg/ml (section 9.2.2). Once the prescribed volume has been drawn into the syringe, an opaque paper shield should be applied to the syringe in order to maintain blinding of staff and/or parents at the bedside.

The use of muscle relaxant prior to tracheal toilet, BAL and or administration of the intervention is at clinical discretion.

Administration: Either with the infant connected to the ventilator, or momentarily disconnected with hand-bagging, the syringe filled with air will be connected to a 5-French catheter end-hole inserted into the endotracheal tube (ETT) for ventilation. Passing the catheter through the suction or sideport into the ETT and advancing the catheter aiming to have the tip of the catheter placed just beyond the tip of the ETT. The insertion length should be calculated from the known length of the ETT (typically cut to reduce dead space) plus the distance from the end of the cut edge of the ETT to the suction/side port). The air will be given slowly as a single bolus directly into the lower trachea (recommended over 0.5 to 3 minutes).

9.4 Unblinding

N.B. Allocation must not be routinely revealed to CTRC personnel. It is to be expected that some site staff may be accidentally unblinded due to unavoidable back-tracking of surfactant up the participant's ETT (see section 7.4).

To maintain the overall quality and legitimacy of the trial, unblinding should occur only in exceptional circumstances when knowledge of the actual treatment is **absolutely essential** for further management of the patient (SPIRIT 2013).

After unblinding the Local Investigator is encouraged to maintain the blind as far as possible. The actual allocation must NOT be disclosed to the participant's family or other study personnel including

IRAS 220853 Page **48** of **87**

other site personnel, monitors, sponsors or project office staff; nor should there be any written or verbal disclosure of the code in any of the corresponding patient documents.

The Investigator may unblind at their discretion without need to contact the CTRC first, but must report all unblinding (with reason) as they occur on the corresponding Unblinding CRF.

Unblinding should not necessarily be a reason for study drug discontinuation.

9.4.1 Emergency Unblinding

If a Local Investigator urgently needs to unblind a participant, they are able to do so by opening the unblinding envelope corresponding to the participant's randomisation number.

Partially completed unblinded envelopes will be provided to all sites. The allocation (poractant alfa or air as placebo), as generated by the WebEZ randomisation system, will be marked on a pre-printed slip inside the envelope by the randomising team member, and the envelope sealed. There will be one partially completed envelope for each patient, with the randomisation number clearly visible on the front of the envelope.

Sealed unblinding envelopes should be stored in a secure location that is readily accessible to PICU staff if the need for emergency unblinding arises.

In the case of any adverse event that requires emergency treatment and there is not sufficient time to unblind using the unblinding envelopes, Local Investigators should assume that the participant has been given poractant alfa (Arm A) and administer treatment accordingly. The treatment for any acute adverse event potentially associated with the study intervention would be the same whether the patient had been given surfactant or air. All adverse events should be reported as per the procedures described in section 10.

9.4.2 Accidental unblinding

If accidental unblinding occurs, this must be reported to the CTRC by use of the Unblinding CRF. When reporting include details about:

- 1. Date of unblinding;
- 2. Detailed explanation of circumstances;
- 3. Recipients of the unblinding information;
- 4. Action to prevent further occurrence, if possible.

9.4.3 Unblinding at Trial Closure

Upon trial closure the blinding of parents and blinded staff remains in effect. Site teams and/or pharmacy departments **should not** disclose treatment allocations on an individual basis.

IRAS 220853 Page **49** of **87**

9.5 Concomitant Medications

No incompatibilities or interactions of Curosurf® with other medications are known. There are therefore no restrictions placed by the trial on the use of concomitant medications in BESS participants.

IRAS 220853 Page **50** of **87**

10 SAFETY REPORTING

10.1 Terms and Definitions

"Adverse Event (AE)"

An adverse event (AE) is any untoward medical occurrence in a subject to whom a medicinal product has been administered, including occurrences which are not necessarily caused by or related to that product.

Therefore an AE is any unfavourable or unintended change in the function (symptoms), structure (signs) or chemistry (laboratory data) in a subject to whom an IMP has been administered, including occurrences which are not necessarily caused by or related to that product.

"Adverse Reaction (AR)"

An adverse reaction (AR) is any untoward and unintended response in a subject to an IMP that is related to any dose administered to that subject.

Therefore an AR is any unfavourable or unintended change in the function (symptoms), structure (signs) or chemistry (laboratory data) in a subject that is related to any dose of an IMP administered to that subject.

"Unexpected Adverse Reaction (UAR)"

An unexpected adverse reaction (UAR) is an adverse reaction the nature and severity of which is not consistent with the information about the medicinal product in question set out in the Investigator's Brochure (IB) or the SPC, which may be referenced where the IMP in question is a product with a marketing authorisation.

"Serious Adverse Event (SAE), "Serious Adverse Reaction, or Unexpected Serious Adverse Reaction"

A serious adverse event (SAE) is an AE, AR or UAR respectively that:

- results in death;
- is life threatening (places the subject, in the view of the Investigator, at immediate risk of death
 from the experience as it occurred this does not include an adverse experience that, had it
 occurred in a more severe form, might have caused death);
- requires hospitalisation or prolongation of existing hospitalisation (hospitalisation is defined as
 an in-patient admission, regardless of length of stay, even if the hospitalisation is a
 precautionary measure for continued observation hospitalisations for a pre-existing
 condition, including elective procedures that have not worsened, do not constitute an SAE);
- results in persistent or significant disability or incapacity (substantial disruption of one's ability to conduct normal life functions);
- consists of a congenital anomaly or birth defect (in offspring of subjects, or their partners, taking the IMP regardless of time of diagnosis);
- other important medical events (these may not result in death, be life-threatening, or require
 hospitalisation, but may be considered a serious adverse event or experience when, based
 upon appropriate medical judgment, they are considered to jeopardise the subject and may
 require medical or surgical intervention to prevent one of the outcomes listed in this definition).

IRAS 220853 Page **51** of **87**

"Suspected Serious Adverse Reaction (SSAR)"

A suspected serious adverse reaction (SSAR) is an adverse reaction that is classed in nature as serious and which is consistent with the information about the IMP in question, which in the case of a licensed product is set out in the SPC for that product, and in the case of any other IMP is set out in the IB relating to the trial in question.

"Suspected Unexpected Serious Adverse Reaction (SUSAR)"

A suspected unexpected serious adverse reaction (SUSAR) is an adverse reaction that is classed in nature as serious and which is not consistent with the information about the IMP in question, which in the case of a licensed product is set out in the SPC for that product, and in the case of any other IMP is set out in the IB relating to the trial in question.

"Reference Safety Information (RSI)"

The reference safety information (RSI) for a trial is the information used for assessing whether an adverse reaction is expected. This is contained in either the IB or the SPC.

10.2 Notes on Adverse Event Inclusions and Exclusions

The below sections provide guidance on what should, and should not be considered as AEs for the purposes of the BESS study:

10.2.1 Include:

- An exacerbation of a pre-existing illness, excluding the current case of bronchiolitis.
- An increase in frequency or intensity of a pre-existing episodic event/condition.
- A condition (even though it may have been present prior to the start of the trial) detected after trial drug administration.
- Continuous persistent disease or symptoms present at baseline that worsen following the administration of the trial treatment, **excluding** the current case of Bronchiolitis.
- Laboratory abnormalities that require clinical intervention or further investigation (unless they
 are associated with an already reported clinical event).
- Abnormalities in physiological testing or physical examination that require further investigation or clinical intervention.
- Injury or accidents.

10.2.2 Do Not Include:

- Widely recognised and documented clinical features of bronchiolitis or outcomes associated with MV that are defined outcome measures in this trial (see section 3.5).
- Medical or surgical procedures* the condition which leads to the procedure is the adverse event; e.g. pneumothorax leading to chest drain placement, here pneumothorax is the event.
- Pre-existing disease or conditions present before treatment that do not worsen.
- Situations where an untoward medical occurrence has occurred, e.g. cosmetic elective surgery.
- Overdose of medication without symptoms or signs**.

IRAS 220853 Page **52** of **87**

* Cosmetic elective surgery is cited here as example of an event that is not reportable as an AE.

** See also section 9.2.4. If overdose occurred with resulting symptoms and signs that met the protocol criteria for AE/AR/SAE/SAR then they should be reported accordingly. Please note that though overdose of medication without symptoms or signs may be excluded from AE reporting this may still require investigation to ensure the protocol and regulatory requirements are met, e.g. for IMP management and administration to ensure participant safety.

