3.4.2 Potential Risks

Administration of poractant alfa (porcine derived surfactant, Curosurf®) in infants with bronchiolitis is well tolerated and considered safe(3). Transient minor adverse reactions associated with administration of poractant alfa for the treatment of neonatal Respiratory Distress Syndrome (RDS) include bradycardia, hypotension, endotracheal tube blockage, and oxygen desaturation. The risk of such events is minimised by tracheal toilet prior to administration of poractant alfa, as recommended in the Summary of Product Characteristics.

Small volume (2x1mL/kg) non-bronchoscopic bronchoalveolar lavage (BAL) procedure on PICU is safe and well tolerated procedure(7). In a published audit of 27 children on PICU who underwent multiple small volume BAL installations (5x1mL/kg) as part of a single routine diagnostic procedure, 7 experienced transient oxygen desaturation requiring temporary increased FiO₂. We will limit BAL sampling to a 2x1mL/kg instillation at each scheduled assessment.

Small volume (1.25mL (range 1.0 to 1.3mL)) blood sampling will be done on infants ventilated at Liverpool and Southampton PICUs and scheduled to coincide with routine blood sampling. Existing vascular access will be used when available. There is no risk of anaemia associated with this limited volume of blood sampling. The sample will be taken from an arterial line if present. If not by standard venesection.

Capillary blood gas sampling (100microliters) or arterial blood gas sampling for subject monitoring will use data from routine blood gas sampling when either is collected within a 2-hour window of a research-scheduled sample. As this is part of standard care no additional risks are expected.

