3.5 Aims & Objectives of Work Package A

351 Aims

- To conduct a multicentre blinded randomised placebo-controlled phase-2 trial of the endotracheal surfactant poractant alfa (CUROSURF®) as therapy for bronchiolitis in critically ill infants.
 - **Hypothesis to test:** Endotracheal surfactant reduces duration of mechanical ventilation by 18 hours (Work package A (WP-A)).
- 2. To evaluate the safety profile in the two treatment groups

IRAS 220853 Page **19** of **87**

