3.6 Outcome measures/endpoints

3.6.1 Primary Outcome/Endpoint

The primary outcome measure will be total duration of MV (hours) from randomisation to final extubation. We will include time off MV due to failed extubation.

Justification: This outcome measure is clinically important, was suggested in both HTA and EME commissioning calls and is valued by our Parent Advisory Group. Reduced duration of MV reduces ventilator-associated morbidity, sedation, muscle relaxants, healthcare costs and bed occupancy at a time of increased seasonal pressure.

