10.2.3 Notification of deaths

There is an overall likelihood of death in all cases of severe bronchiolitis of 1-2%. All deaths that occur during the protocol-specified AE reporting period, regardless of relationship to study drug, must be recorded. All deaths should be reported on a "Serious Adverse Event CRF" and returned to the CTRC within 24 hours.

Death should be considered an outcome and not a distinct event. The event or condition that caused or contributed to the fatal outcome should be recorded as the single medical concept on the appropriate CRF; e.g. death following pneumothorax, here pneumothorax is the event. Generally, only one such event should be reported. The term "sudden death" should only be used for the occurrence of an abrupt and unexpected death due to presumed cardiac causes in a participant with or without pre-existing heart disease, within 1 hour of the onset of acute symptoms or, in the case of an unwitnessed death, within 24 hours after the participant was last seen alive and stable. If the cause of death is unknown and cannot be ascertained at the time of reporting, "unexplained death" should be recorded on the appropriate CRF. If the cause of death subsequently becomes available (e.g. after post-mortem examination), "unexplained death" should be replaced by the established cause of death.

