#### 17.5.2.1. Derivation

The occurrence of any air leaks is recorded on the PICU Discharge/ Day 90 Status CRF and is indicated where the variable PDAIRLKC = "Yes" and the corresponding frequency of these events is expressed by the variable PDALINCI. All occurrences will be summed within patients.

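### Protocol 10.2.2 exempts MV-related outcome measures from AE reporting, yet the protocol's own examples treat pneumothorax as a reportable event

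*Protocol*

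**What the plan says.** Protocol 10.2 sets out what sites should and should not treat as an adverse event in this trial. The first item of the list of things to leave out (10.2.2) reads "Widely recognised and documented clinical features of bronchiolitis or outcomes associated with MV that are defined outcome measures in this trial". Its second half carries a pointer to section 3.5: "outcomes associated with MV that are defined outcome measures in this trial (see section 3.5".

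The second item of that list says that a procedure is not itself the event; the condition behind it is. Its example is "pneumothorax leading to chest drain placement, here pneumothorax is the event". Section 10.2.3, on deaths, uses the same condition: "death following pneumothorax, here pneumothorax is the event".

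Protocol 3.6.2 lists eight safety outcomes. Item 3 is air leak (pneumothorax and pneumomediastinum) up to PICU discharge. Item 4 is *other* adverse and serious adverse events linked to the intervention. Item 5 is replacement of the endotracheal tube.

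The SAP takes these two outcomes from forms other than the AE forms. For air leak (17.5.2.1): "The occurrence of any air leaks is recorded on the PICU Discharge/ Day 90 Status CRF", as a yes/no with a count. For tube replacement (17.5.4.1) the source is a yes/no on the Observations and Outcomes CRF. Each is compared between arms.

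**The concern.** Air leak is a defined outcome measure and is naturally read as associated with mechanical ventilation, so the first item of 10.2.2 appears to tell sites to keep it off the AE form. The very next item, and 10.2.3, tell them that pneumothorax is the event to record. A site that looks up the cross-reference finds no list of outcomes to settle the question.

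The consequence goes beyond tidiness. Under 10.1 a serious adverse event is an adverse event that meets a seriousness criterion, so an event ruled out as an AE is also ruled out as an SAE. It would not reach the 24-hour report (10.7, 10.8.3), the investigator's causality judgement (10.4), the Chief Investigator's expectedness assessment (10.5, 10.10) or SUSAR reporting. What the SAP draws on for air leak instead is a yes/no and a count, with no causality, severity or timing field named. The protocol (9.1) describes this as the first large randomised study of any surfactant in bronchiolitis, so an individual, assessed report of a suspected air-leak reaction matters.

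**Working it through.** No arithmetic is involved; the check is a comparison of texts.

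1. **Which outcomes does the exemption catch?** Of the eight safety outcomes in 3.6.2, items 1 and 2 are defined by an adverse event having occurred, item 4 is AEs and SAEs themselves, item 6 is readmission, and items 7 and 8 are deaths. Air leak (item 3) and tube replacement (item 5) are the two that fit the description of MV-associated defined outcomes and that no other sentence expressly keeps reportable. Deaths are expressly kept: 10.2.3 requires them on the SAE form within 24 hours. So 2 of 8 are affected.

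2. **Does the cross-reference help?** The heading it leads to is "3.5 Aims & Objectives of Work Package A". The outcome measures stand under "3.6 Outcome measures/endpoints". The pointer is wrong, and following it does not show which outcomes are meant.

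3. **Does other text agree with the exemption?** For air leak, three places point the other way:
   - the chest-drain example in 10.2.2;
   - the fatal example in 10.2.3;
   - the word *other* in item 4 of 3.6.2, which follows air leak and so implies that air leak is itself an adverse event.

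   For tube replacement the conflict is milder. Replacement is a procedure, so the second item of 10.2.2 would also leave it off the AE form while keeping its cause reportable.

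4. **Do the general duties settle it?** Sections 8.5 and 10.9 require sites to report all adverse events. They govern what is done with an adverse event, whereas 10.2 governs what counts as one, and neither section says that it overrides 10.2.2. They sharpen the conflict without resolving it.

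5. **Is there an exception for serious or related events?** None is stated in 10.2.2.

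6. **Which air leaks are exposed?** Section 10.7 collects all AEs until 24 hours after the final intervention, adverse reactions until 90 days or hospital discharge, and serious events whenever sites learn of them. A late air leak that is neither serious nor related would be outside AE reporting anyway. The exposed group is air leaks inside the AE window, together with later ones that are serious or related.

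7. **What does the analysis lose?** SAP 17.5.2 and 17.5.4 do not use the AE forms, so those comparisons stand. The tables in SAP 20.2 do, and could hold air leaks from some sites and not from others.

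**The case against.** The strongest reply is that no reasonable site would leave a pneumothorax off the AE form when two worked examples name it as the event and 8.5 and 10.9 ask for everything. That defeats the reading that the rule takes air leak out of AE reporting altogether. The text is contradictory, so the expected result is uneven reporting. It does not show that the text is safe: the exemption is the only sentence that speaks directly about defined outcomes.

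A second reply is that a related air leak is an adverse reaction, and 10.7 requires all adverse reactions. This helps only partly, because 10.4 describes a reaction as an adverse event judged possibly, probably or almost certainly related; the event must first count as an AE.

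A reader might also infer more than the documents support:

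- **Known drug reactions.** Section 3.4.2 says that the transient reactions to poractant alfa "include bradycardia, hypotension, endotracheal tube blockage, and oxygen desaturation". None of these is a defined outcome in 3.6.2. The restriction to defined outcomes can be read as applying to both halves of the 10.2.2 bullet. Section 10.2.1 includes physiological abnormalities that need investigation or intervention, and 10.7 covers adverse reactions. A tube blockage that leads to replacement is the reportable condition under the second item of 10.2.2. The SAP's Treatment CRF codes (17.5.1.1) also treat procedural events as AEs.
- **Reporting delay.** Setting the 24-hour SAE limit against the mean PICU stay of 6.1 days in section 3.2 is not a valid contrast. The 24 hours apply only to serious events (non-serious ones have seven days under 10.8.2), and 6.1 days is a whole admission in a national cohort, not the time from an air leak to discharge.
- **Interim monitoring.** SAP 13.1 omits air leak from its interim report contents, but it lists no adverse events of any kind. Protocol 16.4.3 gives the IDSMC interim safety monitoring and 10.11 provides for reports of serious events. The omission shows nothing specific to this exemption.

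**Conclusion.** The concern holds for air leak and, less sharply, for tube replacement. Protocol 10.2.2 conflicts with its own next bullet, with 10.2.3 and with the wording of 3.6.2, and its pointer is wrong. The gap lies in expedited reporting, causality assessment and AE tabulation. Collection of the two outcomes, their between-arm comparison and the primary outcome are unaffected.

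The size cannot be given as a count: the documents state neither an air-leak rate nor how sites read the rule. If the reading is a site habit, it applies to both arms, because randomisation is 1:1 within site, and the AE tables would be incomplete rather than tilted. If it is decided case by case, that reassurance is lost. For a single serious, related air leak the difference is between full assessment and a tick and a count.

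The conclusion assumes that air leak counts as associated with mechanical ventilation, and that the outcomes meant are those in 3.6. It also rests on the protocol supplied, whose amendment log ends at version 2.0. The SAP cites versions 3.0 and 6.0, so the sentence may since have changed.

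**What to change.** First check whether the current protocol still carries this wording. If it does, revise the outcome-measure part of the first 10.2.2 bullet so that it:

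- points to 3.6 instead of 3.5;
- lists by name the outcome measures, if any, that need no AE/SAE form;
- states that the exemption does not apply to air leak (pneumothorax or pneumomediastinum), nor to any event that is serious or suspected to be related to the intervention;
- says how tube replacement is handled, consistently with the existing rule that the underlying condition is the event.

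Leave the 10.2.1 exclusions for the current bronchiolitis as they are. The new sentence should limit only the outcome-measure exemption. Wording that made worsening of the current bronchiolitis reportable would create a fresh contradiction with 10.2.1.

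The cost is one protocol paragraph, a training note to sites and a few extra AE/SAE forms for events that sites already record elsewhere.
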